4.1 Study Participants

Subjects will be parents/caregivers and their children in grades K-4 in one of three Counties: Cuyahoga County (East Cleveland City School District (ECCSD, Cleveland, OH) and Bedford City School District (BCSD, Bedford, OH)); Cowlitz County (CC, WA); and Lewis County (LC, WA); (See Table 4.1.1 below). The study will be offered to all caregivers and their children including those children with special health care needs. Parent/caregivers and children will be enrolled in the study upon signing the consent/assent form and completing the recruitment and contact form. All enrolled children will receive a dental screening at the beginning of the school year. Following the screening, only parent/caregivers whose child has a tooth with an International Caries Detection and Assessment System (ICDAS) active lesion score of 2 or greater will be randomized and continue further participation in the trial. Caregivers with multiple children in K-4 will receive the same intervention assignment.

Table 4.1.1 School District Information

County	School District	Elementary Schools	K-4 Enrollment
Cuyahoga Co.	East Cleveland City SD	Caledonia, Chambers, Mayfair, Superior	889
	Bedford City SD	Central, Glendale, Columbus, Carywood	1274
Cowlitz Co.	Kelso SD.	Catlin, Wallace	1122
	Longview SD.	Kessler, St. Helens	
Lewis Co.	Central SD.	Jefferson Lincoln	586
	Winlock SD.	Winlock Miller	

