5.4 Treatment Assignment Procedures

5.4.1 Randomization Procedures

Sequence Generation: The study Biostatistician will generate the randomization sequence, which will be loaded into REDCap for allocation. REDCap is a secure, web-based application designed to support remote data capture for research studies, providing: 1) an intuitive interface for validated data entry, 2) audit trails for tracking data manipulation and export procedures, 3) automated export procedures for seamless data downloads to common statistical packages, and 4) procedures for importing data from external sources. Caregivers will be randomly assigned to one of the five study arms in the 17:17:2:2:17 ratio; randomization of caregivers will be stratified by their child's grade level and school. The caregivers with multiple children will receive the same treatment based upon the grade level and school of one of their children, selected at random. Permuted blocks will be used to ensure the allocation of treatment assignments within strata as planned. Only the Biostatistician and the Data Manager will be aware of the blocking scheme and the actual assignments.

Allocation Process: Caregivers will be allocated to study arms using the randomization module provided in REDCap. REDCap uses previously-generated randomization sequences to assign records to study arms, and can support up to 14 stratifying variables. Each unique caregiver ID will be linked to one or more unique child IDs in a one-to-many relationship. As each child record is examined, the corresponding caregiver's study arm assignment will be displayed. If no allocation is found, the study staff will be directed to the randomization form to allocate that caregiver to the correct arm. REDCap will assign each caregiver to a specific study arm in accordance with the pre-determined randomization sequence and the stratifying variables. To assist study staff in quickly processing randomizations, stratifying variables (as well as other basic data) will be prepopulated into REDCap by the Project Coordinators, using information gathered prior to the dental screening and randomization process. REDCap is secured using TLS/SSL, enabling study staff to use it from laptops using public or private wireless connections.

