The sample size was calculated with the following assumptions for the overall effect of the intervention letter: 19% utilization rate for standard letter (Nelson et al. 2012), 37% rate for CSM referral letter alone (based on Medicaid utilization among children: GAO-08-1121, 2008), 57% rate for CSM referral letter + DIG (based on 57% who reported that they took their child to the dentist or had an appointment after receiving the CSM referral letter + DIG in the R34 study). Then, using a two-sided test for equal proportions (namely, a Z test with pooled variance), we find that a sample size of 102 per intervention group per site (thus, 306 subjects per site) will provide 80% power to detect rate differences of 19% versus 37% (as expected for Arm 5 vs Arm 1) or 37% versus 57% (as expected for Arm 1 vs Arm 2) for each site, and 98% power for each of these comparisons using the

combined sample. As siblings (with the same caregiver) may be included in the study, a conservative approach will be to consider the required sample sizes as referring to the number of caregivers. Somewhat greater power will be expected if within-caregiver correlation is less than 1.

For the Ohio site with a total of 889 potential children, we expect 86% to participate (Nelson & Milgrom 2012), with 56% receiving a referral and 5% excluded for emergent needs. From previous [name] study in ECCSD elementary schools we expect 10% of caregivers to have multiple (usually two) children. Thus, an estimated total of 366 caregivers will be available for randomization to the five groups. For the Washington sites, with a total of 1704 potential children, we expect 85% participation (based on 2013 screenings in both districts), with 28% receiving a referral, 5% exclusions for emergent needs, and a 10% reduction in the corresponding number of caregivers due to inclusion of siblings. A total of 347 caregivers will be available for randomization. Even with 5% out of school transfers, the available sample will be adequate for testing the proposed hypothesis. Thus, we expect to randomize 330 caregivers/site to the five study arms to account for any drop-outs at randomization and maintain the required power for the trial.

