12.4 Final Analysis Plan

Primary Statistical Analysis: Descriptive statistics will include frequencies (categorical variables) and means (continuous variables) of baseline covariates among the five intervention groups. Chi-square tests (for categorical variables) and t-tests (for continuous variables) will be performed to test for group differences (by site and overall). In our primary analysis, we will fit multivariate generalized linear (specifically, logistic regression) models with dental care receipt as the (binary) outcome and the child as the unit of analysis (as receipt of dental care will be determined for each child). A generalized estimating equations (GEE) approach (with an exchangeable working correlation structure) will be used to allow for correlations among multiple children for a given caregiver. Separate models will be fit for each site as well as overall. The models will include two indicator variables representing the three interventions. Each model will include an a priori selected set of

baseline variables (listed below) and, for the overall model, an indicator variable for site. Secondarily, we will fit a model with a site by intervention group interaction, and the latter will be tested to formally assess possible intervention effect heterogeneity over sites.

We will also consider working correlation structures (e.g., alternating logistic regressions) that allow for second-level clusters, namely schools (within which the first-level cluster, caregiver, is nested). We will determine final models based on the quasi-likelihood information criterion (QIC). Intervention (and other covariate) effects will be tested using generalized score statistics.

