Given the parameter estimates from the above models, we use a model-based standardization approach (Albert et al. 2011) to estimate relative risks (i.e., the ratio of the probabilities of dental usage for a given pair of interventions). A bootstrap approach will be used to obtain a 95% confidence interval for each relative risk. Significance will be determined using a gatekeeper approach to hypothesis testing. Specifically, we will first test for a difference in dental care receipt rates for S vs CSM+DIG (at the 0.05 nominal alpha level). If (and only if) this test is significant, we will proceed to test S vs. CSM alone and CSM vs CSM+DIG (both at the 0.05 nominal alpha level). We will use a similar approach for testing for each site. We will start by testing (for a given treatment comparison) an overall effect (stratifying over sites) at the 0.05 nominal alpha level. If (and only if) this is significant, we will then test (for the same treatment comparison) the effect within each site (at the 0.05 nominal alpha level). A 0.05 family-wise error level is attained in this approach assuming that a (true) effect for S vs. CSM+DIG implies a (true) effect for either S vs. CSM or CSM vs. CSM+DIG (or both), and that an overall effect implies an effect in one or both sites (which is logically the case).

To test the effect of the targeted component (timeline), we will fit the same multivariate generalized linear (specifically, logistic regression) models mentioned above with additional indicator representing reduced text.

Adjustment for Baseline Characteristics: Estimated intervention effects (described above) will be adjusted for the following baseline socio-demographic variables: child's age, race, and caregiver SES, education, and marital status.

Model Assumptions: We will assume that the probabilities of dental care receipt follow the selected logistic regression model (controlling for covariates) mentioned above. We assume that the outcomes for different caregivers (or different schools if a correlation structure for two cluster levels is used) are independent.

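### Randomization is stratified by school and grade, but the primary mean model has no school term and leaves school to an optional, QIC-chosen correlation structure, which gives up a little site-level power if schools differ

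*Combined protocol and SAP*

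**What the plan says.** Section 5.4.1 states that "randomization of caregivers will be stratified by their child's grade level and school". It adds: "Caregivers will be randomly assigned to one of the five study arms in the 17:17:2:2:17 ratio". On blocking it says "Permuted blocks will be used to ensure the allocation of treatment assignments within strata as planned", but gives no block size.

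Section 12.4 makes the primary analysis a logistic GEE model with the child as the unit and caregiver as the exchangeable cluster, fitted separately by site and overall. Besides the arm indicators, each model carries the "baseline variables (listed below) and, for the overall model, an indicator variable for site". The listed variables are child's age, "race, and caregiver SES, education, and marital status". No school or grade term appears, and in the separate site models the site indicator drops out as well.

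School is mentioned once for the primary outcome. The plan will also consider correlation structures with schools as a second cluster level above caregivers, and QIC decides the final model. The paragraph on model assumptions adds that, under such a structure, independence is assumed between schools rather than between caregivers. Effects are tested with generalized score statistics, and relative risks receive bootstrap intervals.

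**The concern.** An analysis should normally reflect the factors on which allocation was balanced. If school predicts receipt of care, for example through local access to dentists, two things follow from omitting it. Outcome variation that the model could explain stays in the error, which costs power. And if blocking has balanced the arms within schools, the usual variance overstates the true variability of the arm contrast, so the test rejects less often than 5% under the null.

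The cost would fall mainly on the site-level tests, for which Section 12.2 claims only 80% power. A further issue is that a confirmatory, gatekept test should not depend on a data-driven choice of how school is handled, particularly when one candidate rests on very few independent units.

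**Working it through.** **1. The plan's own figure.** Section 12.2 claims 80% power with 102 per group per site, and 98% combined. With a two-sided pooled Z test at 0.05:
- 80% power needs 97 per group for both 19% vs 37% and 37% vs 57%. Adding 5% for transfers gives 97 × 1.05 ≈ 102.
- At a full 102 per group, power is 82.2% and 82.1%. At 204 it is 98.3% for both.

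The stated figures reproduce.

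**2. Strata against block size.** The ratio sums to 17+17+2+2+17 = 55, so 55 is the smallest block that holds it exactly. Table 4.1.1 lists 8 Ohio schools (the East Cleveland row, for example, reads "Caledonia, Chambers, Mayfair, Superior") and 6 or 7 in Washington, where the Lewis County rows are ambiguous as extracted. Section 12.2 says "we expect to randomize 330 caregivers/site to the five study arms".
- Ohio: 8 × 5 grades = 40 strata; 330/40 ≈ 8.3 caregivers each.
- Overall: 14–15 schools × 5 = 70–75 strata; 660/75 to 660/70 ≈ 8.8 to 9.4 each.

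Most blocks of 55 would never fill, so balance within strata would be weak.

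**3. Approximate size with school omitted, age and site included.** True size ≈ 2Φ(−1.96/√(1 − R²f)).
- R² ≈ 0.19 × 0.81 × SD² = 0.1539 SD² is the share of outcome variance due to school.
- f is the share of between-stratum imbalance removed by blocking: about 1 for near-perfect balance. For blocks of 55 and 9.4 caregivers per stratum, f = 1 − (55 − 9.4)/54 ≈ 0.16.

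| School SD (logit, assumed) | R² | Size, near-perfect balance | Size, blocks of 55 |
|---|---|---|---|
| 0.3 | 0.014 | 4.8% | 4.97% |
| 0.5 | 0.039 | 4.6% | 4.93% |
| 0.8 | 0.099 | 3.9% | 4.82% |

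Simulation of the overall model (660 caregivers, 14 schools, 10,000 runs, robust Wald test) gave 5.0 / 4.9 / 5.2% with blocks of 55 and 5.0 / 4.7 / 4.1% with idealised blocks of 3.

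**4. Site-level simulation.** Settings: 306 caregivers in the three main arms, 8 schools × 5 grades, one child per caregiver, child's age in the comparator model, 3,000 runs per case. Power is for 19% vs 37%. Entries are for assumed school SDs of 0.4 / 0.7 / 1.0.

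| Block | Size without strata, % | Size with school + grade, % | Power without, % | Power with, % | Gain, points |
|---|---|---|---|---|---|
| 3 | 4.6 / 3.6 / 3.4 | 5.3 / 5.1 / 5.1 | 84.5 / 82.2 / 83.6 | 85.7 / 84.9 / 88.7 | 1.2 / 2.7 / 5.1 |
| 6 | 4.8 / 4.9 / 4.0 | 5.3 / 5.9 / 6.0 | 84.0 / 83.8 / 82.5 | 85.0 / 86.6 / 87.0 | 1.0 / 2.8 / 4.5 |
| 51 | 5.3 / 4.8 / 5.0 | 6.2 / 5.5 / 5.5 | 82.4 / 82.7 / 82.1 | 82.8 / 85.3 / 87.1 | 0.4 / 2.6 / 5.0 |

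Monte Carlo error is √(0.05 × 0.95/3000) ≈ 0.4 points for size.

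Two further checks used the full block of 55 with age in the model:
- Wald test, five arms, 330 caregivers: size 4.8 / 5.2 / 5.1% without strata and 5.4 / 5.9 / 5.7% with them; power gain about 0, 2 and 5 points.
- Robust score test, closer to the plan's statistic: size 5.6 / 4.6 / 4.2% without strata, against 4.7 / 4.5 / 3.9% with tight blocks. Under either blocking the power gain was about 1, 2–3 and 4 points, with adjusted size 4.8–5.9%.

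**5. The school-cluster route.** With 14 schools as the independent units, an uncorrected robust Wald test had size 8.3–9.5% in the simulations of step 3. The planned generalized score test was not simulated in this configuration and may behave better. A site model would have only 6 to 8 schools.

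**The case against.** The strongest reply is that the plan does not ignore school. Section 12.4 allows schools as a second cluster level, and because arms vary within schools, such a structure could recover some of the lost precision. That is fair as far as it goes. But the option is only to be considered, its adoption depends on QIC, and it moves the independence assumption to a handful of schools. It is not a committed school term in the mean model.

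Second, age is a close stand-in for grade in K–4, and the socio-demographic covariates may absorb part of any school difference. The point about age stands, which is why school is the substantive omission. How much the other covariates absorb cannot be judged from the documents.

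Third, a reader might infer that the primary tests are conservative as a matter of fact. The documents do not support this: they give neither a block size nor a school effect. With blocks of 55 the shortfall in size is negligible to small, and under the school-cluster option the error could run the other way.

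Fourth, a reader might infer that site-level power falls below the claimed 80%. The simulations do not show this: power without the strata was 82–85%. No bias or false-positive risk from omitting school was shown, and part of the power gain reflects adjusted tests running slightly above 5%.

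**Conclusion.** The mismatch between the randomization and the primary mean model is in the text, and it is worth correcting because the remedy is cheap. Its consequence is modest. Omitting school costs about 1 to 4–5 points of site-level power for assumed school SDs of 0.4 to 1.0, and this holds broadly whatever the block size. Conservatism is clear only with tight blocks, or to a small extent with large school effects. The separate weakness is that the handling of school in a confirmatory test is left to QIC.

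These sizes rest on assumed school effects, the Ohio layout of 8 schools, one child per caregiver, and age as the only other baseline covariate in the simulated site models.

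**What to change.** Amend Section 12.4 and the SAP as follows:
- Enter school as a fixed effect in every primary model; in the overall model it replaces the site indicator.
- Either add grade as a fixed effect or state that child's age replaces it.
- Keep caregiver as the GEE cluster, and draw bootstrap samples of caregivers within school.
- Do not let QIC decide how school enters the primary test. A school-cluster model can stay as a sensitivity analysis, with a small-cluster correction.
- Record the block size.

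The relative risk remains standardized over the sample, so its interpretation is unchanged.

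The cost is SAP wording and extra parameters. For Ohio this is 8 − 1 = 7 for school, or 7 + 4 = 11 with grade. In the overall model, 14–15 schools need 13–14 terms in place of one for site, a net 12–13, or 16–17 with grade. Ohio averages 306/8 ≈ 38 main-arm caregivers per school, and even at the 19% control rate that is about 7 events, so the terms should usually be estimable; a rule for pooling very small schools should be stated. Size may run slightly above nominal, up to about 6% in simulation, which favours using school plus age if the site models prove strained.

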Washington Sites: These sites will use the same recruitment approach as ECCSD. The study intends to recruit 1452/1708 K-4 children (85%). In a recent screening with a similar rural population (Jefferson and Morrow Counties, OR), 85% of families agreed to participate with only a single notice home and no personal contact or follow-up. In an earlier study with a similar rural population, UW investigators recruited 76% of eligible families (Weinstein, Spiekerman & Milgrom 2009). Based on 28% caries rate, we expect that 407/1452 recruited children will be screened positive for untreated caries. 5% of the children who are positive will be excluded because of emergent needs. Further 10% will be caregivers with multiple children. Thus, an available pool of 348 caregivers will be eligible for randomization.

Due to lower than expected enrollment in both the Ohio and Washington sites, we plan a second year of recruitment to include Bedford School District and East Cleveland School District (only KG and perhaps other grades if they did not enroll in the first year). For the Bedford School District, 1274 KG-4th grade children were enrolled during 2015-2016 school year in four elementary schools; 80% Black; 67% economically disadvantaged eligible for free/reduced cost school lunch program. Bedford is quite similar to East Cleveland. Using our experience from the first year of recruitment we expect that out of the 1274 Bedford school children, about 764 will receive baseline screening (60% participation rate). Of 764 children, about 267 caregivers will be randomized (taking into account 30% multiple children and 50% caries rate). Similarly we expect about 50 caregivers will be randomized in East Cleveland. Between Bedford and East Cleveland School Districts, we expect to screen about 950 children in 2016-2017 school year. Of the 950 screened we expect to randomize 317 caregivers. So we can meet our recruitment goal of 258 caregivers that is necessary to complete the study.

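### The site-by-intervention test has no school-year term, yet the only districts named for year 2 are in Ohio, so a year or district change in intervention effect would read as site heterogeneity

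*Combined protocol and SAP*

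**What the plan says.** - **Original timetable.** Section 4.2 describes one school year at both sites, with screening in October 2015 and final exams in May 2016.
- **Extension.** Section 5.3 gives the reason as "Due to lower than expected enrollment in both the Ohio and Washington sites" and continues: "we plan a second year of recruitment to include Bedford School District and East Cleveland School District". No Washington district is named. East Cleveland's second-year intake is described as "only KG and perhaps other grades if they did not enroll in the first year", so that district recruits in both years. Bedford enters as the new district.
- **Numbers.** For Bedford, "out of the 1274 Bedford school children, about 764 will receive baseline screening (60% participation rate") and "about 267 caregivers will be randomized (taking into account 30% multiple children and 50% caries rate"). About 50 more are expected from East Cleveland, making 317. The section concludes: "So we can meet our recruitment goal of 258 caregivers that is necessary to complete the study".
- **Analysis.** In section 12.4 the overall model carries a site indicator, and the interaction model is secondary: "a model with a site by intervention group interaction, and the latter will be tested to formally assess possible intervention effect heterogeneity over sites". Adjustment is for the child's age and race and the caregiver's SES, education and marital status. Neither school year nor school is in that list. Schools may enter as a second cluster level in the working correlation, and a school random effect is optional for the questionnaire outcomes.
- **Randomization.** Section 5.4.1: "randomization of caregivers will be stratified by" grade level and school.
- **Meaning of site.** Table 3.2.1 lists site as an urban/rural moderator.

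**The concern.** The extension made site and school year overlap, and section 12.4 was not adapted to it. On the districts named, every 2016-17 caregiver is in Ohio. The Ohio effect is therefore an average over two school years and two districts, whereas the Washington effect comes from one year.

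The interaction test compares these two effects and reads any gap as heterogeneity over sites. The documents give reasons why the effect might not be constant across the Ohio cohorts: most of the second cohort comes from a district new to the study, and the rest from schools that already took part, mainly in kindergarten. What is at stake is the only formal test of whether the letters work differently in the urban and rural populations. The treatment effects themselves are not at risk.

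**Working it through.** **1. The plan's recruitment figures reproduce.** 1274 × 0.60 = 764 screened in Bedford. 764 × 0.50 × 0.70 = 267 randomized. 267 + 50 = 317. With a total of 660 (Protocol Summary) and 258 still needed, year 1 implies 660 − 258 = 402. Year 2 is 258/660 = 39% of the sample. Bedford is 267/317 = 84% of expected year 2.

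**2. Share of Ohio that is second-year.** Let w be Washington's part of the 402, which the documents do not give. Ohio totals (402 − w) + 258 = 660 − w, so the share is s = 258/(660 − w). I bound w by letting neither site exceed its planned 330 in year 1.

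| w (assumed) | Ohio total | s |
|---|---|---|
| 72 | 588 | 44% |
| 150 | 510 | 51% |
| 201 (even split) | 459 | 56% |
| 250 | 410 | 63% |
| 330 | 330 | 78% |

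If all 317 are randomized, the range is 317/647 = 49% to 317/389 = 81%. Washington's share is 0% throughout.

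**3. What the interaction estimates.** The check uses the three main arms at 17/55 of caregivers each, one child per caregiver, no covariates and no drop-out. First-year rates at both sites are those of section 12.2: 19% (standard), 37% (CSM), 57% (CSM+DIG). There is no true site difference. With no year term, the fitted Ohio rate in an arm is (1 − s) × year-1 rate + s × year-2 rate.

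*Case A: the effect changes.* Second-year rates are assumed to be 19%, 28% and 38%, which halves the risk differences. With w = 201, Ohio CSM+DIG = 0.438 × 0.57 + 0.562 × 0.38 = 0.463. Its logit is −0.147, against logit(0.57) = 0.282 in Washington. The standard arm is 19% everywhere, so the site-by-CSM+DIG coefficient is −0.147 − 0.282 = −0.43, where the truth is 0.

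*Case B: only the level changes.* Add 0.55 log-odds to every arm in year 2. Ohio standard becomes 0.438 × 0.19 + 0.562 × 0.289 = 0.246. Ohio CSM+DIG becomes 0.438 × 0.57 + 0.562 × 0.697 = 0.641. Relative to Washington these are shifts of 0.328 and 0.299 log-odds, so the coefficient is 0.299 − 0.328 = −0.03.

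Fitting the logistic models to these expected cells gives:

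| | w = 150 | w = 201 | w = 250 |
|---|---|---|---|
| A, as written: coefficient | −0.39 | −0.43 | −0.48 |
| A, as written: 2-df rejection rate | 9% | 11% | 14% |
| A, cohort main effect added: coefficient | −0.37 | −0.42 | −0.47 |
| A, cohort and cohort-by-arm added: coefficient | 0.00 | 0.00 | 0.00 |
| A, cohort and cohort-by-arm added: rejection rate | 5% | 5% | 5% |
| B, as written: coefficient | −0.03 | −0.03 | −0.03 |
| B, as written: rejection rate | 5% | 5% | 5% |
| SE as written (Case A) | 0.54 | 0.49 | 0.47 |
| SE with cohort and cohort-by-arm | 0.60 | 0.58 | 0.60 |

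**4. Why the larger model works.** There are nine cells: Washington year 1, Ohio year 1 and Ohio year 2, by three arms. The model with site, cohort, arm and both interactions has nine parameters, all estimable. Its site-by-arm coefficient is therefore exactly the 2015-16 contrast between the sites. Check of its SE at w = 201: n per arm = 201 × 17/55 = 62.1 at each site, and SE = √[2 × (1/(62.1 × 0.19 × 0.81) + 1/(62.1 × 0.57 × 0.43))] = √[2 × (0.1046 + 0.0657)] = 0.58.

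**The case against.** The strongest reply is that randomization within grade and school already protects the trial. Arms are compared within school, so a better or worse year for access to care moves all arms together. Case B shows that this leaves the interaction test nearly untouched. That stands, and it narrows the point to a change in the intervention *effect*. Nothing in the documents shows that such a change occurred. The halving in Case A is an assumption chosen to show scale.

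Also correct:

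- The test is secondary and plays no part in the gatekeeper sequence.
- Schools are not ignored, since they may enter the working correlation. That affects standard errors and weighting but does not remove the confounding.
- Site was never a pure urban/rural contrast. The populations also differ in race and ethnicity, and the dental guide's resource section is adapted to each site.

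A reader might infer that the design cannot separate site from year. It can: Ohio recruited in both years, so the missing terms are estimable and a concurrent subset exists. A reader might also infer that the by-site treatment effects are biased by year. They are not, because both arms of each comparison come from the same randomized strata.

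Nor do the documents rule out second-year recruitment in Washington; they simply name none. Finally, the Supplemental Materials page lists a Statistical Analysis Plan stored separately and not included here. If it already has these terms, the point is closed.

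**Conclusion.** The point holds in a limited form. As planned, the pooled site-by-intervention test cannot tell a site difference in intervention effect from a difference between school years or between East Cleveland and Bedford. Under the assumptions of Case A, with 150 to 250 first-year Washington caregivers, the spurious coefficient is 0.39 to 0.48 log-odds in size and the test rejects 9% to 14% of the time instead of 5%. If the effect is constant across years and districts, there is essentially no harm.

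It would go too far to say that the site contrast is mainly a contrast of years. With an even first-year split, 44% of Ohio is concurrent with Washington, and the 78% extreme requires Washington to have met its full target, which fits poorly with a stated shortfall at both sites. This is an inexpensive improvement to a secondary analysis, and it leaves the primary comparisons as they are.

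**What to change.** In section 12.4:

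1. Repeat the site-by-intervention test on the 2015-16 cohort, or add cohort (2015-16, 2016-17) *and* cohort-by-intervention terms to the pooled interaction model. Report the result beside the pooled test. A cohort main effect alone is not enough.
2. Rest any statement about site heterogeneity on the concurrent contrast, and say that the pooled test is confounded with school year.
3. State that the cohort contrast within Ohio is mostly East Cleveland against Bedford, so it must not be read as a calendar effect.
4. Adjust the outcome models for school, the randomization stratum. Each school lies in one site, so school indicators replace the site main effect in the overall model; the site-by-intervention term stays.

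The cost is a few sentences of analysis text, with recruitment year taken from enrolment dates and school from the randomization record. The downside is a less precise interaction estimate, with the SE rising from about 0.47-0.54 to 0.58-0.60 under the splits assumed above.
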